## **9.2 ADVERSE DEVICE EFFECT (ADE) DEFINITION**

Adverse event related to the use of an investigational medical device.

Note 1: This definition includes adverse events resulting from insufficient or inadequate instructions for use, deployment, implantation, installation, or operation, or any malfunction of the investigational medical device.

Note 2: This definition includes any event resulting from use error or from intentional misuse of the investigational medical device.

## **9.3 DEVICE DEFICIENCY (DD) DEFINITION**

Inadequacy of a medical device with respect to its identity, quality, durability, reliability, safety or performance. Note: Device deficiencies include malfunctions, use errors, and inadequate labeling.

## **9.4 SERIOUS ADVERSE EVENT DEFINITION**

Serious Adverse Events (SAEs) are AEs that lead to:

- death
- a serious deterioration in the health of the subject that:
  - results in a life-threatening illness or injury
  - results in a permanent impairment of a body structure or function (e.g., blindness)
  - requires in-subject hospitalization or prolongation of existing hospitalization
  - results in medical or surgical intervention to prevent permanent impairment to a body structure or a body function
- fetal distress, fetal death, or a congenital abnormality or birth defect
- a potentially sight-threatening condition
- or is another important medical event.

## **9.5 UNANTICIPATED PROBLEM DEFINITION**

An unanticipated problem is defined as any incident, experience, or outcome that meets all of the following criteria:

- Unexpected/unanticipated – (in terms of nature, severity, or frequency) given (a) the research procedures that are described in the protocol-related documents (protocol, ICD, product labeling, IB); and (b) the characteristics of the subject population being studied; and

- Related or possibly related to the participation in the research (possibly related means there is a reasonable possibility that the incident, experience, or outcome may have been caused by the drugs, devices, or procedures involved in the research); and
- Suggests that the research places participants or others at a greater risk of harm [new or increased risk (including physical, psychological, economic, or social)] than was previously known or recognized.

## 9.6 IDENTIFICATION AND COLLECTION

Identification and collection of an AE begins after informed consent has been obtained and documented. Standard sources of identifying AEs include:

- direct observation by the Investigator or study team member
- asking the study participant a specific question (e.g., “Since your last visit, have you experienced any problems with your eyes or vision?”)
- unsolicited volunteering of information by the study participant (e.g., “Doctor, I have had numerous headaches since I started using this lens.”)

Ocular AEs, ocular SAEs, and systemic SAEs observed or elicited by the Investigator, reported by the subject, or resulting from a test result, etc., occurring during the clinical investigation must be documented. During the study, the Investigator should treat the study subject as appropriate to ensure his/her safety and welfare. Refer to Section 7.8.1 for additional information pertaining to ongoing AEs at subject exit.

Pre-existing conditions will not be considered AE/SAEs but will be collected at the Preoperative Visit as medical history. A worsening of a pre-existing condition during the study should be documented as an AE and evaluated accordingly.

Hospitalization is a criterion for assessment of seriousness. Hospitalization in the absence of a medical AE is not in itself an AE. For example, the following reports of hospitalization without a medical AE should not be considered either an SAE or an AE:

- Planned hospitalization for a pre-existing condition without serious deterioration in health (e.g., planned knee replacement surgery)
- Social admission (e.g., subject has no place to sleep)
- Administrative admission (e.g., for yearly physical exam or elective procedures not related to the study)
- Optional admission not associated with a precipitation medical AE (e.g., for elective cosmetic surgery)

### 9.6.1 EVALUATIONS

When evaluating AEs, the Principal Investigator or delegated MD sub-Investigator must determine if the event is serious, assess the severity of symptoms, the relationship of the event to the device or study protocol, using the following guidelines:

## 1. Severity

**Mild:** subject awareness of a sign or symptom that is easily tolerated, requires no treatment, and does not interfere with subject's daily activities

**Moderate:** subject awareness of a sign or symptom which may be a low level of concern to the subject and may interfere with daily activities, but can be relieved by simple therapeutic care

**Severe:** a sign or symptom that interrupts the subject's daily activity and requires systemic therapy or other treatment

## 2. Relationship (Causality) to Study Device or Study Protocol

**Related:** There is at least a reasonable possibility that the AE/SAE is related to the study device or study protocol. Reasonable possibility means that there is evidence to suggest a causal relationship between the study device or study protocol and the AE.

**Unrelated:** There is little or no reasonable possibility that the AE/SAE is related to the study device or study protocol. This assessment implies that the AE/SAE has little or no temporal relationship to the study device and/or a more likely or certain alternative etiology exists.

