### 8.6.1 ADVERSE EVENTS (AE)

For each adverse event, the number of reports, number and percent of subjects with the AE, and number and percent of eyes with the AE will be summarized at the operative visit and each postoperative visit by lens group. Serious ocular AEs and the non-ocular serious AEs will be summarized in the same manner. Additionally, for each device-related AE reported during the study will be presented in the same manner.

Each ISO-defined cumulative and persistent adverse event at Postop Month 6 will be summarized using the count and percent of the subjects reported with such event along with the one-sided lower 95% confidence limit of the percent based on the binomial distribution. If the lower limit is below the ISO specified SPE rate for the respective AE, then it will be concluded that the LAL does not have a rate higher than the corresponding SPE rate specified by the ISO.

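### The single causality call pools device and protocol, so as written it cannot supply the device-related AE table or the adverse device effect class

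*Combined protocol and SAP*

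**What the plan says.** Section 9.6.1 tells the investigator to assess "the relationship of the event to the device or study protocol, using the following guidelines". The guideline has two levels. Related opens with "There is at least a reasonable possibility that the AE/SAE is related to the study device or study protocol". Unrelated begins with the same pooled object, device or protocol, but then adds: "This assessment implies that the AE/SAE has little or no temporal relationship to the study device and/or a more likely or certain alternative etiology exists". Its temporal criterion therefore names the device only.

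Two other places need a narrower answer:

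- Section 8.6.1, after describing the AE tables by lens group, adds: "Additionally, for each device-related AE reported during the study will be presented in the same manner".
- Section 9.2 defines an ADE as "Adverse event related to the use of an investigational medical device". Note 1 extends this to events arising from "insufficient or inadequate instructions for use, deployment, implantation, installation, or operation", and to malfunctions. Note 2 adds: "This definition includes any event resulting from use error or from intentional misuse of the investigational medical device".

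Section 7.8.1 uses ADE status, alongside ocular serious AEs, as a criterion for continued follow-up when an event is unresolved at exit.

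**The concern.** The analysis asks for a classification that the recorded judgement does not contain. The protocol prescribes cataract surgery, perioperative medication, viscoelastic and, for some light treatments, pupil dilation. Section 9.1 counts events caused by the procedures as AEs, so each one needs a causality call. An investigator who attributes an early postoperative event to surgery can mark it Related because it follows from the protocol, even though the lens and the light treatment had no part in it. If the Related field is used directly for the device-related table in Section 8.6.1, that event appears there.

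At stake is whether that table can be interpreted, and whether the ADE class is assigned consistently. For a lens that is altered by ultraviolet light after implantation, readers will look at exactly this table.

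**Working it through.** The plan gives no figure for device-related or procedure-related AE rates, so there is no stated number to reproduce. The check is mainly a comparison of the texts.

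**1. What each place requires**

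| Place | What the event must be related to | Control lens covered? |
|---|---|---|
| 9.6.1, Related | Device or protocol, one call | Not stated |
| 9.6.1, Unrelated, temporal part | Device only | Not stated |
| 8.6.1, device-related table | Device | Apparently, since tables are by lens group |
| 9.2, ADE | Use of the investigational device, with Notes 1 and 2 | No |

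**2. Can the pooled call supply the others?** An event can be related to the device only, to the protocol only, to both, or to neither. The pooled call returns Related for the first three and Unrelated for the fourth. The table in 8.6.1 needs the first and third. A record of Related does not say which of the three applies, and no visible rule resolves it.

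**3. Is the scale itself even?** Take an event caused by a protocol test long after implantation. It is Related under the first definition because the protocol caused it. The temporal part of Unrelated points the other way, because the event is remote from the device. Likewise, a surgical cause may be read as part of the protocol (Related) or as an alternative etiology to the device (Unrelated). Two investigators could score the same event differently.

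**4. Are surgical events simply outside the ADE class?** No. Notes 1 and 2 of Section 9.2 bring in events from inadequate implantation instructions and from use error. Separating device from surgery therefore takes a judgement on each event, which is a further reason to record it.

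**5. Is the direction of distortion fixed?** For one event type that either cause can produce, let d be the device-related rate and q the procedure-related rate, taken as independent. The recorded rate is 1 − (1 − d)(1 − q). The inputs below are assumptions, used only to show the sign.

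- Device-only rates of 8% (LAL) and 2% (Control) differ by 6.0 points.
- With q = 10% in both arms: LAL 1 − 0.92 × 0.90 = 17.2%; Control 1 − 0.98 × 0.90 = 11.8%. The difference is 5.4 points, so it shrinks. Over q = 5% to 30% it runs from 5.7 down to 4.2 points.
- With q = 15% (LAL) and 10% (Control): LAL 1 − 0.92 × 0.85 = 21.8%; Control 11.8%. The difference is 10.0 points, so it widens. At q = 20% and 10% it is 14.6 points.

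Either case is possible. Surgery is common to both arms, but only LAL subjects attend the extra adjustment and lock-in visits.

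**6. What uses the causality call?** Section 8.6 describes the safety outcomes as descriptive. The primary safety endpoint (Section 5.2) sets LAL rates of ISO-defined events against the ISO reference rates without a causality filter. The all-AE and serious-AE tables in 8.6.1 do not use causality either.

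**The case against.** The strongest reply is that little depends on this field. It is right that lens- and UV-specific harm is captured elsewhere: the phototoxicity criteria in Section 7.3.2.2, the listing of reasons for acuity loss in 8.6.2 (including light treatment), the UV-associated fundus changes in 8.6.7, and the attribution of secondary surgical interventions to optical properties in 8.6.12. None of these gives device causality for AEs in general, so they limit the consequence without removing the gap.

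A reader might infer four stronger things, and the documents do not support them.

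- *That a shared surgical background dilutes a LAL excess.* This assumes equal procedural rates in both arms, and the LAL-only visits could do the opposite. Section 8.6.1 also reports by event type, so a wound leak does not mask erythropsia. No test of device-related AEs is planned, so an argument from precision or power has no planned use.
- *That the trial's data cannot separate the causes.* The AE form is not shown and part of Section 9.1 is blacked out. The statement holds only for the visible text.
- *That every surgical event is Related and none is an ADE.* The alternative-etiology clause lets some be scored Unrelated, and Section 9.2 counts some as ADEs.
- *That the pooled call decides follow-up after exit.* Section 7.8.1 does not say which field sets ADE status, and over-inclusion would only lengthen follow-up.

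**Conclusion.** The point holds as a mismatch between a stated rule and the output that depends on it. Section 9.6.1 collects one pooled answer; Sections 8.6.1 and 9.2 each need a narrower one, and they differ from each other on the Control lens. The descriptive device-related table may mix device and procedural events, and the ADE class has no stated source.

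The size cannot be estimated from the documents, and the direction of any distortion between arms is open. The primary safety endpoint and the all-AE tables are unaffected, so this is a worthwhile clarification and not a threat to the main safety conclusion. The conclusion rests on the visible text. If the AE form already records separate calls, what remains is to align 9.6.1 and 8.6.1 with it.

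**What to change.** - **Section 9.6.1 and the AE form** (unless the form already does this): record separate related or unrelated calls for (a) the implanted IOL, (b) the light delivery device or light treatment, LAL group only, and (c) surgery or other protocol procedures. Allow more than one to apply.
- **Unrelated:** word the temporal criterion to match each call.
- **Section 8.6.1:** define device-related as (a) or (b), including the implantation-instruction and use-error events that Notes 1 and 2 of Section 9.2 count as device effects. Tabulate events related only to (c) separately.
- **Control arm:** present events related to the Control lens as comparator-device-related, and reserve ADE for the LAL and light delivery device, as Section 9.2 does.
- **Events already marked Related:** query the investigator for (a), (b) or (c) before the final analysis.

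The cost is two further causality items on the form, short edits to two sections and a modest query load. The queries also mean re-attribution by investigators who know the lens assignment, since masking covers only the designated Month 6 measurements. The report should say which calls were obtained by query. No extra subjects, visits or procedures are needed.

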### 9.7 SAE REPORTING

The site should report any event to the Sponsor and its representative in an expedited manner if it meets the criteria for an ocular or non-ocular SAE and/or is an IOL explant from a study eye. Expedited reporting is calling or e-mailing the Sponsor and its representative within 48 hours of becoming aware of the event. Contact details are as follows:

[REDACTED]

When reporting an SAE to the Sponsor and/or its representative, the site should forward any supporting documents along with the SAE Report Form to the Sponsor and its designee within 5 days of the initial communication. All supporting information must have all protected health information (PHI) removed and the subject ID added. Sites must also report these events to the reviewing IRB/IEC per its established reporting procedures.

### 9.8 UNANTICIPATED ADVERSE DEVICE EFFECT (UADE) REPORTING

An investigator shall submit to the Sponsor and to the reviewing IRB/EC a report of any Unanticipated Adverse Device Effect (UADE) occurring during an investigation as soon as possible, but in no event later than 10 working days after the investigator first learns of the effect. As soon as notification of a potential UADE is received by the Sponsor, an investigation will be initiated to determine if the event is a UADE. If the event is confirmed to be a UADE, the regulatory authorities, all other participating Investigators and each reviewing IRB/EC must be notified within 10 working days of the initial report from the site. If it is determined that the UADE represents an unreasonable risk to study subjects, the study

must be terminated within 5 working days following the decision, and no later than 15 working days after first learning of the UADE.

### **9.9 DEVICE DEFICIENCY (DD) REPORTING**

All device deficiencies (DDs) should be reported to the Sponsor without unjustified delay. The Sponsor will assess the DD to determine whether it led to an adverse event (AE). AEs resulting from DDs will be documented, assessed, and reported in accordance with adverse event guidelines. DDs that did not lead to an adverse event but could have led to a Serious Adverse Device Effect (SADE) will be reported in the future PMA as required in ISO 14155.

### **9.10 UNANTICIPATED PROBLEM (UP) REPORTING**

If an incident, experience, or outcome meets all 3 criteria of the unanticipated problem definition described in section 9.5, then a UP should be reported to the Sponsor without unjustified delay. Furthermore, reporting of an unanticipated problem to the IRB should occur within 10 business days of discovery by the Investigator or Sponsor Representative reporting the event. The IRB will report unanticipated problems to the appropriate regulatory agencies and to the institutional official/sponsor, as appropriate.

### **9.11 PREGNANCY**

During the study, all female subjects of childbearing potential should be instructed to contact the investigator immediately if they suspect they might be pregnant (e.g., missed or late menstrual period). Female subjects who become pregnant during the study will be followed until completion of pregnancy. Every effort will be made to obtain the health status of the mother and infant or fetus (in cases of miscarriage or therapeutic abortion) at term. Pregnancy itself is not considered an AE.

All confirmed pregnancies must be immediately reported to the Sponsor within 48 hours of the investigator's awareness of the pregnancy.

### **9.12 POTENTIAL ADVERSE EVENTS**

The following have been identified as potential adverse events for all cataract surgeries including the LAL. Please notify the Sponsor regarding any events that may be occurring more frequently than your customary rates, or more frequently than expected at your site.

Infection, inflammation, hypopyon, endophthalmitis, infectious keratitis, hyphema, retinal detachment or other retinal problems including cystoid macular edema and epiretinal membranes, toxic anterior segment syndrome, glaucoma, corneal endothelial damage, vitritis, corneal edema which may require correction with a corneal transplant, lens dislocation out of the posterior chamber, pupillary block, striation on the lens with or without visual sequelae, iritis, synechiae, ptosis, wound leak, flat anterior chamber, increased astigmatism, rupture of the capsule, iris prolapse, vitreous in the anterior chamber, and retained pieces of the lens in the eye. These adverse events may result in total loss of vision or the loss of an eye.

Secondary surgery may be required after the cataract surgery to treat surgical complications. Additionally, a posterior capsulotomy may be required to treat posterior capsular haze after

the cataract surgery. Visual problems after cataract surgery may include halos, glare, ghost images, and/or double vision which may be worse after implantation of an EDF type lens. Additionally reduced contrast sensitivity is also possible after implantation of an EDF type lens. These and other complications may result in permanent poor vision.

Additional specific risks of the LAL include:

The LAL must be implanted following specific surgical procedures. If these procedures are not followed by the surgeon, the lens may become scratched or improperly placed in the eye and may need to be explanted prior to light treatments. In order to perform the lens adjustment or the lens lock-in procedures, the subject's pupil needs to be adequately dilated. If this cannot be accomplished for any reason, additional eye drops, injections into the eye, or surgery may need to be utilized to adequately dilate the pupil. If the pupil cannot be adequately dilated after these types of treatments, the LAL may need to be explanted. An unpredicted change in vision can occur resulting from ocular exposure to daylight or any other UV source before the LAL is locked-in. The light treatments may not improve vision and/or manifest refraction, and the adjustment/lock-in procedure may make vision worse, such that it may be necessary to remove and replace the LAL. Vision loss may be permanent and may not be improved by replacing the LAL. There is a potential risk for UV-induced damage to the eye, including the cornea and retina, which may be permanent. UV light can sometimes cause a reactivation of previous herpes virus infection in the eye. A reactivation of herpes virus can cause scarring of the cornea, blurred vision, eye pain, extreme light sensitivity, permanent loss of vision, and possible need for corneal transplant. Temporary or persistent erythropsia and/or temporary or persistent color vision deficiency may occur. Corneal dryness and corneal abrasions from the lens used for adjustment and lock-in can occur. After the lens adjustment(s) or after the lens lock-in procedures, discomfort, itching and light sensitivity may occur. In cases where a spherocylinder adjustment is performed, it is possible that visual disturbances may occur if the IOL rotates or if the correction is not performed on the correct axis of astigmatism.

### **9.13 POTENTIAL COVID-19 RISKS**

If a COVID-related public health emergency declaration is in place at the time of the study, the study site should take appropriate measures in a clinic setting to minimize spread of the virus in conformance to professional society guidelines and applicable guidance from the states and counties in which the sites are located.

In addition, the study informed consent has been updated to outline additional subject risks that are related to trial participation during an ongoing COVID-19 pandemic. They are as follows:

- The subject will be exposing themselves to added risks due to the COVID-19 pandemic (including possible transmission of Coronavirus infection, and possible further complications including but not limited to hospitalization and/or death) beyond the risk of adverse events due to the investigational device and/or procedure(s).

- The subject will be at higher risk in an ophthalmic clinical study because of the close contact they will have with health care professionals during their procedure and assessment (since the examiner must make measurements close to their face), in addition to the need for multiple follow-up visits/exams which will expose them to other patients and/or healthcare professionals who could be transmitting the virus even if they do not have symptoms.
- Subjects may still be at risk even if appropriate measures are taken to minimize risks in conformance to FDA guidance, American Academy of Ophthalmology guidelines, and guidance from the states and counties in which the study clinics are located.
- Subjects should be aware that potential disruptions to the IDE study may be necessary due to current or future pandemic-related emergency restrictions, such as possible disruption of the study as a result of COVID-19 control measures that may lead to delays in scheduled follow-up visits.
- Subjects who experience an adverse safety event (i.e. a safety complication) may experience a delay in seeing their doctor either due to COVID restrictions and/or due to their own concerns or fears about COVID risk, that could potentially lead to a dangerous situation with serious permanent visual side effects including loss of vision. Adverse outcomes typically require subjects to return for additional and possibly frequent follow-up office visits and examinations; thus increasing their COVID-related risks.
- Subjects who have contracted COVID-19 or feel ill with flu-like symptoms during their participation in the study will not likely be permitted to continue routine scheduled study follow-up, thereby increasing the risk that diagnosis and treatment of potential adverse safety outcomes could be missed or delayed.

RxSight will interact with study sites based on geographic location to determine which sites may be more impacted by COVID-19 during a particular period of enrollment and potentially subject to study disruptions. Sites may be restricted from enrolling in the study for a period of time based on local disease conditions. RxSight will work with sites to ensure that light treatments are continued when possible during any period of study disruptions, while maintaining subject safety.

